3.2 Protocol violations

- Timing of inclusion: the patients should be included within 6 hours after the vasospasm diagnosis confirmation by CTA, which may be delayed relative to CTA acquisition, when a re-analysis by an expert is required. A delay of more than 6 hours is considered as a protocol violation and constitute an exclusion criteria.
- Study medication infusion: the study medication should be administered for at least 48 hours. However it could be suspended for several hours (in case of intolerance), without protocol violation, if the study medication is reinfused.
- Any administration of intravenous milrinone is a protocol violation, but intra-arterial use during angiography, is allowed.
- Study medication weaning is protocolized through progressive tapering of infusion rate, decrement of 5 ml/h every 24-48 hours. A quicker tapering is considered as a protocol deviation, but not a violation. Study medication may be stopped after D7 CTA, if the vasospasm did not improve at all.

3.3 Analysis populations

- The intent-to-treat (ITT) population includes all the randomized patients except those who withdrew consent. Patients who were lost to follow up will still be considered in the ITT population through imputation processes, described below.
- The per-protocol population (PP) includes all patients in the ITT population without protocol violations (mainly open-label IV milrinone infusion or

 CHU ANGERS <small>CENTRE HOSPITALIER UNIVERSITAIRE</small>	 Statistical analysis plan	N° EudraCT 2019-002145-37 CT Number : 2024-515994-83-00 SAP V1.0 Date : 15/01/2026
---	--	---

definitive stop of study medication within the first 48 hours). The protocol violations will be determined before locking the database by a group of experts.

4 Section 4 – Trial Population

4.1 Eligibility

Patients hospitalized for acute aSAH will be included if a cerebral vasospasm occurred, suspected because of a clinical deterioration and/or high blood flow velocity on TCD examination and confirmed by CTA. The inclusion /randomization will be done within 6 hours after vasospasm diagnosis (i.e., when the study investigator get the information, sometimes after re-analysis of the CTA by an expert). Inclusion and exclusion criteria are presented below:

4.1.1 *Inclusion criteria:*

- Adult patients hospitalized for aneurysmal aSAH
- First episode of vasospasm, with a diagnosis confirmed on CTA
- Delay between diagnosis of vasospasm and inclusion \leq 6 hours
- Informed consent from the patient, a legal representative or emergency procedure

4.1.2 *Exclusion criteria:*

- Initial Glasgow score at 3 with a bilateral mydriasis
- Moribund patient
- Contraindication to Milrinone
- Cerebral infarction in the vasospasm area already present on the CT-scanner at the time of diagnosis (lack of expected benefit of treatment in this case according to medical judgement)
- Cardiac failure requiring inotrope administration at the time of randomisation
- Uncontrolled elevated intra-cranial pressure (i.e. ICP>25 mmHg for more than 20 minutes)
- Patient with flutter or cardiac arrhythmia (atrial fibrillation) poorly tolerated

 CHU ANGERS <small>CENTRE HOSPITALIER UNIVERSITAIRE</small>	 Statistical analysis plan	N° EudraCT 2019-002145-37 CT Number : 2024-515994-83-00 SAP V1.0 Date : 15/01/2026
---	--	---

- Major metabolic disturbance (uncorrected hypokalaemia <3 mmol/L)
- Non-affiliation to French health care coverage
- Pregnant, breastfeeding or parturient woman
- Adult deprived of their liberty by judicial or administrative decision
- Adult under compulsory psychiatric care
- Adult patient protected under the law (guardianship or trusteeship)
- Inclusion in an interventional study using Milrinone, or evaluating a treatment of cerebral vasospasm or with the same primary endpoint (mRS at 3 months)

4.2 Withdrawal/Follow-up

When a patient is loss of follow-up their 3-month mRS will be missing. We anticipate few events that would make it impossible to measure the primary outcome, based on our cohort experience. However, in case of such missing data, imputation processes will be carried out to allow an ITT analysis. The considered imputation processes are described below.

For patients who withdraw consent, those who have not been randomized will be excluded from the analysis, but described in the CONSORT flowchart. For the patients who withdraw consent after, all the data obtained on the inclusion visit (see below) will be kept to allow the imputation process, and the safety data will be also analyzed.

4.3 Baseline characteristics

Baseline characteristics of randomized patients include age; sex, comorbidities, usual medication, admission ECG, hemoglobin at patient's admission, parameters of secondary brain injury (natremia min/max, body temperature min/max, mean arterial pressure min/max, ICP min/max), SAH characteristics/grade (WFNS initial score, Fisher class), Initial treatment of aneurysm (embolization and/or surgery), Consciousness at inclusion.

 CHU ANGERS <small>CENTRE HOSPITALIER UNIVERSITAIRE</small>	 Statistical analysis plan	N° EudraCT 2019-002145-37 CT Number : 2024-515994-83-00 SAP V1.0 Date : 15/01/2026
---	--	---

5 Section 5 – Analysis

5.1 Outcome Definition

5.1.1 Primary outcome:

The primary endpoint is the proportion of good functional outcome (defined as a modified Rankin score (mRS) ≤ 2) at 3 months, obtained by centralized standardized phone interview of the patient or his/her relative.

Modified Rankin Score is rated as follow:

- 0 = No symptoms,
- 1 = No significant disability. Able to carry out all usual activities, despite some symptoms,
- 2 = Slight disability. Able to look after own affairs without assistance, but unable to carry out all previous activities,
- 3 = Moderate disability. Requires some help, but able to walk unassisted,
- 4 = Moderately severe disability. Unable to attend to own bodily needs without assistance, and unable to walk unassisted,
- 5 = Severe disability. Requires constant nursing care and attention, bedridden, incontinent,
- 6 = Death.

5.1.2 Secondary outcomes:

- a) Glasgow Outcome Scale Extended (GOSE) is obtained by centralized standardized phone interview of the patient or his/her relative done at 3 and 6 months. The GOSE is a global scale for functional outcome, categorized in 8 categories from 1 (death) to 8 (upper good recovery).
- b) EuroQOL Quality of Life Scale 5-Dimension 5-Level (EQ-5D) is a questionnaire is conducted at baseline, 3 and 6 months. It consists of a short and simple 5-part questionnaire and a visual analogue scale (VAS). It may be self-administered, completed by interview or via a proxy respondent, and is used to value and describe health states. The questionnaire data is reported as an index value - a continuous

 CHU ANGERS <small>CENTRE HOSPITALIER UNIVERSITAIRE</small>	 Statistical analysis plan	N° Eudract 2019-002145-37 CT Number : 2024-515994-83-00 SAP V1.0 Date : 15/01/2026
---	--	---

fractional outcome with boundaries between zero and one. Zero represents the worst health status and 1 the best. The EQ-VAS (visual analogue scale) is a self-administered visual scale in which respondents rate from 0 to 100 (worst and best state of health respectively) their perceived health-related quality of life at the time of response. In analyses including non-survivors, deceased patients will be given the lowest score. The EQ-5D will be analyzed as a variation from baseline at 3 and 6 months.

c) Mortality will be analyzed until 6 months.

5.1.3 Tertiary outcomes:

- a) ICU and hospital length of stays
- b) Percentage of patients alive and at home at 3 and 6 months. It will also be analyzed as the number of days alive and at home at day 90 (DAAH90).
- c) angiographic success will be assessed by the evaluation of vasospasm severity on inclusion, D7 and D14 (if available) CTA. Vasospasm will be quantified according to the reduction of cerebral arteries diameter evaluated on a semi-quantitative scale as: absent, light, mild, moderate or severe, (compared to the diameter measured on admission CTA).
- d) Number of therapeutic arteriography
- e) The volume of cerebral necrosis will be measured on magnetic resonance imaging (MRI) obtained between 3 and 6 months following aSAH
- f) on adverse events evaluated until 48 hours after study medication stop.
- g) The treatment tolerance will be evaluated by assessing the rate of patients with hemodynamic intolerance defined as the need for catecholamines introduction or doses increased by 50% within the first 24 hours of study medication infusion ; and of metabolic intolerance defined as the rate of patients with dysnatremia, (ie natremia<135 mmol/L or >155 mmol/L) occurring during the administration of study medication.

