2.2 Randomization

Randomization is performed using a web-based system (Clinsight® software). Patients are randomly assigned in a 1:1 ratio to one of the two groups using a minimization algorithm based on three determinants: study site, initial World Federation of Neurological Surgeons (WFNS) grade ([1 or 2] vs [3 to 5], higher scores being indicative of more severe aSAH), state of consciousness at the time of vasospasm diagnosis (conscious vs unconscious, including patients under sedation).

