2.5 Timing of outcome assessment

2.5.1 Primary outcome:

- a) Modified Rankin Scale (mRS) score [3 months]

2.5.2 Secondary outcomes:

- a) Modified Rankin Scale (mRS) score [6 months]; Glasgow Outcome Scale Extended (GOSE) [3 & 6 months]
- b) EuroQOL Quality of Life Scale 5-Dimension 5-Level (EQ-5D-5L) [6 months]
- c) Mortality [in hospital and 6 months]

2.5.3 Tertiary outcomes:

- a) ICU and hospital length of stays [in hospital]
- b) Angiographic success on CTA [D7 and D14 (if available)]
- c) Number of therapeutic arteriography [D14]
- d) Cerebral necrotic volume assess by magnetic resonance imaging (MRI) between 3 and 6 months following aSAH [6 months]
- e) Adverse events [study medication infusion, maximum 14 days]

 CHU ANGERS <small>CENTRE HOSPITALIER UNIVERSITAIRE</small>	 Statistical analysis plan	N° EudraCT 2019-002145-37 CT Number : 2024-515994-83-00 SAP V1.0 Date : 15/01/2026
---	--	---

3 Section 3: Statistical Principles

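### EQ-5D is analysed as a raw change from baseline with deaths scored at the follow-up floor, so death need not be the worst result and precision can be lost against a baseline-adjusted follow-up score

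*SAP*

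**What the plan says.** SAP section 5.1.2 b) defines the EQ-5D outcome.

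- **Collection.** The EQ-5D "is a questionnaire is conducted at baseline, 3 and 6 months".
- **Index scale.** "Zero represents the worst health status and 1 the best".
- **Deaths.** "In analyses including non-survivors, deceased patients will be given the lowest score". Table 1 lists the exclusion of deceased patients only as a sensitivity analysis, so the main EQ-5D analysis includes them.
- **Analysed quantity.** "The EQ-5D will be analyzed as a variation from baseline at 3 and 6 months".
- **Respondent.** Of the EQ-5D: "It may be self-administered, completed by interview or via a proxy respondent". Of the scale: "The EQ-VAS (visual analogue scale) is a self-administered visual scale in which respondents rate from 0 to 100".

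Elsewhere in the SAP:

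- Section 2.2 makes consciousness a minimisation factor ("conscious vs unconscious, including patients under sedation"), so unconscious patients are enrolled. Their share is not given.
- Section 5.2.2 models the EQ-5D score at 3 and 6 months by proportional odds. Table 1 names a linear model with a mean difference. Neither mentions change.
- The adjustment set in section 5.2 and Table 1 is centre, WFNS and consciousness. Baseline EQ-5D is not in it, nor among the baseline characteristics of section 4.3.
- Section 2.5.2 gives the timing as "EuroQOL Quality of Life Scale 5-Dimension 5-Level (EQ-5D-5L) [6 months" only. Sections 1.2.2, 5.1.2 and 5.2.2 give 3 and 6 months.
- Section 3.1 provides a p-value at the 0.05 level for secondary outcomes.

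**The concern.** Giving deaths the floor value is meant to make death the worst result. That works on the follow-up score. Once baseline is subtracted, the result for a death depends on where the patient started, and the ordering of death and survival is no longer protected. A proportional odds model uses only ordering, so under section 5.2.2 the misordering would enter the test itself.

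Two further costs follow from using change. A raw change carries the full baseline variation into the outcome, whereas a covariate removes only what baseline predicts. A change also needs a baseline value for every patient, and for the EQ-VAS the SAP does not say who supplies it when the patient is unconscious or sedated.

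At stake are the meaning and precision of a quality-of-life comparison that will be reported with a p-value.

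**Working it through.** **1. The plan's own figure.** The SAP gives no SD, correlation or power for EQ-5D. Its only sample size is for the primary outcome (section 2.3: 35% against 50%, two-sided 5%, power 80%):

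n = [1.96·√(2·0.425·0.575) + 0.842·√(0.35·0.65 + 0.50·0.50)]² / 0.15² ≈ 169.3, so 170 per arm and 340 in total.

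This reproduces the SAP. It is used below only to supply 170 per arm.

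**2. Ranking of deaths.** With follow-up set to 0, a death from baseline b has change 0 − b = −b. A survivor going from B to f has change f − B. The death ranks above the survivor whenever B − f > b.

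| Patient (illustrative) | Baseline | Follow-up | Change |
|---|---|---|---|
| Dies | 0.10 | 0 | −0.10 |
| Survives | 0.80 | 0.50 | −0.30 |
| Dies | 0.40 | 0 | −0.40 |
| Survives | 1.00 | 0.50 | −0.50 |
| Dies | 0 | 0 | 0 (no change) |

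The second pair shows that the reversal does not need a near-floor baseline. It can occur whether baseline describes the state before the bleed or at inclusion, and between two patients with the same consciousness status.

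**3. Precision.** Let the follow-up SD be σ, the baseline SD kσ and their correlation r, all within levels of the adjustment factors. Residual variances under a linear model:

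- follow-up alone: σ²
- raw change: σ²(1 + k² − 2rk)
- follow-up adjusted for baseline: σ²(1 − r²)

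Change minus adjusted is σ²(k − r)², which is never negative. So change is never more precise than the adjusted analysis. With equal SDs (k = 1) the ratio is 2(1 − r)/(1 − r²) = 2/(1 + r). Change is worse than follow-up alone only when r < k/2, that is r < 0.5 for equal SDs.

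**4. Size.** Assumptions not in the SAP: σ = 0.35, true difference 0.10, k = 1, all 170 per arm analysed. Power = Φ(0.10/SE − 1.96), with SE = (residual SD)·√(2/170).

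| r | Variance ratio, change to adjusted | Change | Adjusted | Follow-up alone |
|---|---|---|---|---|
| 0 | 2.00 | 46% | 75% | 75% |
| 0.2 | 1.67 | 55% | 77% | 75% |
| 0.5 | 1.33 | 75% | 86% | 75% |

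At r = 0.2, the change SD is 0.35·√1.6 = 0.443, SE 0.0480, and Φ(2.08 − 1.96) = 55%. The adjusted SD is 0.35·√0.96 = 0.343, SE 0.0372, and Φ(2.69 − 1.96) = 77%.

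**5. Smaller baseline SD.** With k = 0.5 and r = 0.2, the change variance factor is 1 + 0.25 − 0.20 = 1.05. The SD is 0.359, SE 0.0389, and power Φ(2.57 − 1.96) = 73%, against 77% adjusted. Most of the loss disappears.

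**6. EQ-VAS baseline.** The general sentence on respondents allows a proxy and can be read to cover both parts of the instrument. The sentence on the VAS calls it self-administered. On the second reading, no unconscious patient can supply a baseline VAS. Imputation would then have nothing observed in that stratum to learn from and would extrapolate from conscious patients.

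**The case against.** **Lowest score could mean the lowest change.** Then death would be worst by construction. The SAP does not say so. The sentence follows the descriptions of the index and the VAS, so the follow-up score is the natural reading. One clarifying sentence would answer the ranking point, but not the precision point.

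**Adjustment for consciousness removes cross-stratum comparisons.** In part it does: if unconscious patients all sat near 0 at baseline, change in that stratum would nearly equal the follow-up score. Baselines can still vary within a stratum, and reversals remain possible there.

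**Under Table 1's linear model, randomisation keeps the mean difference in change unbiased.** This stands. There the cost is noise, and missing baselines where they occur. The ranking defect bears on the ordinal model of section 5.2.2.

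Stronger readings that a reader might infer, and that the SAP does not support:

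- *The change is undefined for many patients.* The questionnaire may be answered by proxy, section 5.3 plans multiple imputation, nothing says unconscious patients are dropped, and their share is not stated. What remains is the tension over the self-administered VAS.
- *Baseline is an acute-phase measurement near the floor.* The SAP does not say which state the baseline index describes, and the protocol is not shown. The ranking argument does not need this.
- *Power is lost in general.* Against follow-up alone there is no loss at r = 0.5 with equal SDs, and above that the change score is more powerful. Change can never beat the baseline-adjusted analysis, and it is clearly worse only when r is low and the baseline SD is not small.

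**Conclusion.** The point holds in limited form. On the natural reading of section 5.1.2, a death's change is minus its baseline, so death is not always the worst result. This rests on arithmetic and on that reading of the death rule, not on assumed data.

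The precision loss against a baseline-adjusted follow-up score depends on assumptions: 55% against 77% power at r = 0.2 with equal SDs, SD 0.35, a difference of 0.10 and 170 per arm, but 73% against 77% if the baseline SD is half as large. These figures apply to a linear analysis and to no other.

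The baseline VAS source for unconscious or sedated patients is unclear, and the number affected cannot be derived from the SAP. Sections 5.1.2, 5.2.2 and Table 1 also disagree on the analysed variable and model, and section 2.5.2 on the time points. The primary analysis and its sample size are untouched. The text should be corrected before database lock.

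**What to change.** 1. In section 5.1.2, delete the statement that EQ-5D is analysed as variation from baseline. Analyse the 3- and 6-month index and VAS values themselves, with deaths at the lowest value of each.
2. Adjust for centre, WFNS and consciousness, and add baseline EQ-5D as a covariate, with a missing indicator where it was not obtained. State which health state baseline describes, who may answer, and whether a proxy may complete the VAS.
3. Name one main model in both section 5.2.2 and Table 1. With follow-up values analysed, either an ordinal or a linear model keeps death at the bottom. Keep the analysis excluding deceased patients as a sensitivity analysis.
4. Bring section 2.5.2 into line with sections 1.2.2, 5.1.2 and 5.2.2 on 3 and 6 months, and give the time points in Table 1.

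The cost is SAP wording only, with no new data and no change to sample size. The downside is that no within-patient change is reported as an outcome.

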2.1 Trial Design

MiVAR is a multi-center, double blinded, randomized, placebo-controlled trial that compares the effect of IV milrinone vs placebo (saline), started within 6 hours of the vasospasm confirmation using an computed tomography angiography (CTA), on 3-months function outcomes, in patients with cerebral vasospasm following aSAH.

2.1.1 *Trial interventions*

Eligible patients are randomly assigned to receive either milrinone or placebo within 6 hours after confirmation of the vasospasm diagnosis on a CTA. Study medications are prepared by unblinded nurses or pharmacists not involved in patients care. The study drugs are diluted according to the patient's body weight, so that infusion rates are identical in the two groups for all patients (i.e. an infusion rate of 10 ml per hour corresponds to 0.1 µg/kg/min of milrinone). Milrinone and saline solution are identical in appearance, thereby ensuring blinding of patients, nurses, physicians and outcome assessors.

- **Milrinone group:** milrinone is administered intravenously as a bolus of 0.1 mg/kg over 30 minutes followed by a continuous infusion at a rate of 1 µg/kg/min. In the absence of improvement, the infusion rate may be increased to 1.5 µg/kg/min.
- **Placebo group:** placebo (normal saline) is administered intravenously at the same infusion rate as milrinone.
- **Both groups:** in both groups, induced hypertension with norepinephrine is recommended, along with maintenance of normovolemia. Oral nimodipine is also recommended through D21 after aSAH. Persistence of vasospasm should be assessed at least twice daily by clinical evaluation and/or transcranial doppler (TCD)

 CHU ANGERS <small>CENTRE HOSPITALIER UNIVERSITAIRE</small>	 Statistical analysis plan	N° EudraCT 2019-002145-37 CT Number : 2024-515994-83-00 SAP V1.0 Date : 15/01/2026
---	--	---

examination. In absence of improvement, arteriography for mechanical and/or pharmacological dilatation is recommended.

Duration of treatments

- Study drug weaning is initiated after 48 hours of infusion, with gradual dose tapering in decrement of 0.5 µg/kg/min steps), once vasospasm is controlled. Study medication is discontinued after 7 days in absence of effect on the D7 CTA or on D14.

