5.4 Harms

Adverse Event Reporting

- Expected Serious Adverse Events (eSAE). These events have been defined a priori and are being collected and reported as study outcomes and as such will not be labelled nor reported a second time as serious adverse events.
- Unexpected Serious Adverse Events (uSAE). All uSAEs are to be brought to the attention of the site PI (following site specific standard operating procedures). Causality of the uSAE should be adjudicated by the site PI. All possibly or related uSAEs are to be reported in the

Data Collection Forms (both study arms) as described in this section:

o Monitoring and reporting should begin on the first day of study intervention and continue until either:

- the uSAE has been resolved
- 48 hours post study medication stop or death whichever occurs first
- if the uSAE remains ongoing at 3 months it will be reported as such

o Supporting source documentation of all reported uSAEs must be submitted for additional and final central adjudication.

o Abnormal laboratory results do not need to be recorded unless considered by the investigator to be relevant in terms of subject or trial safety (or in relation to a serious adverse event that is being reported).

 CHU ANGERS <small>CENTRE HOSPITALIER UNIVERSITAIRE</small>	 Statistical analysis plan	N° Eudract 2019-002145-37 CT Number : 2024-515994-83-00 SAP V1.0 Date : 15/01/2026
---	--	---

- Serious Adverse Event Reporting. All reportable unexpected SAEs must be reported to the Coordinating Centre within 24 hours of the site's knowledge of the unexpected SAE. The Study Chair and/or Study Steering Committee will review all unexpected SAE's received from the sites. If an unexpected SAE is confirmed, a document summarizing the SAE will be distributed to participating sites. Sites should follow the guidelines of their local REB with respect to the submission of SAEs that occur at the site as well as SAE Notifications.
- All reportable unexpected SAEs will be described with the presentation of the main results

 CENTRE HOSPITALIER UNIVERSITAIRE	 Statistical analysis plan	N° Eudract 2019-002145-37 CT Number : 2024-515994-83-00 SAP V1.0 Date : 15/01/2026
--	---	---

	Main analysis	Sensitivity analyses for the main analyses	Additional analyses	Adjustement**
Primary outcome				

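### The adverse-event outcome has two conflicting windows, both ending by reference to drug stop; dysnatraemia is compared as a simple proportion over a variable on-drug period; and the harms analysis set is not settled

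*SAP*

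**What the plan says.** **Window.** SAP section 2.5.3 e) gives the timing as "Adverse events [study medication infusion, maximum 14 days", that is, on-infusion only. Section 5.1.3 f) describes the same tertiary outcome as "on adverse events evaluated until 48 hours after study medication stop" and states no cap. Section 5.4, which covers unexpected serious adverse events only, lists three end points as alternatives: "the uSAE has been resolved"; "48 hours post study medication stop or death whichever occurs first"; and "if the uSAE remains ongoing at 3 months it will be reported as such".

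**What sets drug stop.** Section 2.1.1 says "Study drug weaning is initiated after 48 hours of infusion", on condition that vasospasm is controlled, with discontinuation otherwise tied to the day 7 angiogram or to day 14. Section 3.2 allows interruption for intolerance, and section 3.3 foresees a definitive stop within the first 48 hours.

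**Which harms are modelled.** Section 5.1.3 g) counts dysnatraemia only while study drug is being given. Section 5.2.3 analyses it by a logistic model, and Table 1 by a log-binomial model with a risk ratio and 95% CI. Haemodynamic intolerance uses the first 24 hours of infusion. Unexpected serious adverse events are to be described, and Table 1 has no adverse-event row.

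**Analysis set.** The ITT population of section 3.3 "includes all the randomized patients except those who withdrew consent", and section 5.2 makes ITT the default unless otherwise specified. For patients who withdraw after randomisation, section 4.2 says "the safety data will be also analyzed". The Table 1 footnote defines ITT as all randomised patients. No safety population is defined.

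**The concern.** Two analysts working from this SAP could produce different adverse-event tables, one stopping with the infusion and one including the following 48 hours.

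The window is also not fixed by design. It closes when the drug is stopped, and drug stop reflects how the patient responds to and tolerates the treatment. If the arms differ in infusion length, a proportion of patients with an event mixes the daily risk with the number of days watched. An arm watched for fewer days looks safer at the same daily risk, and harms that appear after an early stop are not counted.

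For the analysis set, the question is whether events already recorded in patients who later withdrew consent enter the harms tables. The text gives two answers.

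**Working it through.** **1. The windows side by side.** Days observed per patient (death aside), for a given infusion length:

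| Infusion (days) | Section 2.5.3 | Section 5.1.3 f) |
|---|---|---|
| 1 | 1 | 3 |
| 2 | 2 | 4 |
| 7 | 7 | 9 |
| 14 | 14 | 16 |

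The difference is always 2 days. The drug-stop limb of section 5.4 agrees with section 5.1.3. Its resolution and 3-month limbs read as follow-up of an event already under way.

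**2. Effect of unequal on-drug time on dysnatraemia.** The SAP gives no infusion duration by arm and no dysnatraemia risk, so both are assumed. With a constant daily hazard h, the same in both arms, and T days on drug, the proportion with at least one event is 1 − exp(−hT).

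For T = 4 and T = 7 days:

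| h per day | 4 days | 7 days | Risk ratio (4 vs 7) |
|---|---|---|---|
| 1% | 3.9% | 6.8% | 0.58 |
| 2% | 7.7% | 13.1% | 0.59 |
| 5% | 18.1% | 29.5% | 0.61 |
| 10% | 33.0% | 50.3% | 0.65 |

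At 5%: 1 − exp(−0.20) = 0.181; 1 − exp(−0.35) = 0.295; 0.181/0.295 = 0.61.

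The result depends on the gap assumed. At 5% per day, 6 vs 7 days gives 25.9% vs 29.5%, a risk ratio of 0.88. Equal durations give 1.00.

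**3. What a rate does with the same data.** Expected days at risk up to the first event are (1 − exp(−hT))/h. At h = 0.05 this is 0.181/0.05 = 3.63 days for T = 4 and 0.295/0.05 = 5.91 days for T = 7. First events per day at risk are then 0.181/3.63 = 0.05 and 0.295/5.91 = 0.05, a rate ratio of 1.00. Under constant risk, the person-time analysis removes the artefact.

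**4. Patients affected by the choice of set.** Section 2.3 gives 35% vs 50%, two-sided 5% error and 80% power. The pooled-variance two-proportion formula returns 170 per arm, 340 in total, as stated. Inflating for 5% withdrawals, 340/0.95 = 358, against a planned 360. The number at issue is at most 0.05 × 360 = 18:

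- If section 3.3 governs and every withdrawal is a consent withdrawal: about 18 left out.
- If section 3.3 governs and only some are consent withdrawals: fewer than 18.
- If section 4.2 or the Table 1 footnote governs: 0.

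**The case against.** The strongest reply is that the problem is narrow. Adverse events and tolerance are tertiary, and section 3.1 limits p-values to primary and secondary outcomes. Unexpected serious adverse events are only described, haemodynamic intolerance already has a fixed window, and mortality is followed to 6 months whatever happens to the drug. That leaves dysnatraemia, a tolerance measure for which an on-treatment window is a defensible choice; Table 1 also plots daily minimum and maximum sodium by group. All of this stands, and it limits the reach of the point. It does not reconcile sections 2.5.3 and 5.1.3, and an on-treatment window still needs a denominator that reflects time on treatment.

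Four stronger readings are tempting, and the document does not support them.

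- *All stated windows are tied to drug stop.* Two limbs of section 5.4 are not, and that section concerns unexpected serious events rather than the adverse-event outcome as a whole.
- *Harms are in fact compared over unequal exposure in favour of milrinone.* No duration by arm is given, and the direction is open. Section 2.1.1 lets patients without effect stop after day 7 while others may continue to day 14, so a more effective arm could be watched for longer. At 5% per day, 14 vs 7 days gives 50.3% vs 29.5%, a risk ratio of 1.70 the other way.
- *The trial would declare false significance on harms.* No p-value is planned for these outcomes. A confidence interval is, and it would be centred on the distorted ratio.
- *Withdrawn patients are dropped from safety.* Section 4.2 can be read as the exception that section 5.2 allows for, and the Table 1 footnote includes everyone randomised. Nor does the SAP say that withdrawals are caused by harm.

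**Conclusion.** The point holds in a limited form. The adverse-event outcome has two incompatible windows, 48 hours apart. Both end by reference to drug stop, a post-randomisation event that depends on response and tolerance, and the SAP gives no exposure adjustment for it. Among the modelled harms, only dysnatraemia is affected. With assumed durations of 4 vs 7 days and an equal, constant daily risk of 1% to 10%, its risk ratio would be 0.58 to 0.65 instead of 1. The distortion shrinks with the gap and disappears when durations are equal. Unequal exposure is therefore a risk that the plan leaves open, and not an established bias.

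The harms population is contradictory across sections 3.3, 4.2 and the Table 1 footnote. Between 0 and about 18 patients are affected, the upper figure requiring that section 3.3 overrides the other two and that all the planned 5% are consent withdrawals.

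Neither issue touches the primary analysis. Both change which events and patients appear in the safety tables, and both can be settled before database lock.

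**What to change.** 1. State one adverse-event window in the same words in sections 2.5.3, 5.1.3 and 5.4, matching what has been collected. In section 5.4, separate the end of collection from the follow-up of events still ongoing.
2. Beside the proportions, report adverse events and dysnatraemia as events (or first events) per patient-day at risk, by arm, with a rate ratio and 95% CI. Where the data already held allow it, a common fixed window is an alternative. Tabulate infusion duration by arm so that readers can judge how far exposure differed.
3. State that harms are analysed in all randomised patients who received study drug, including data retained from those who later withdrew, and make sections 3.3, 4.2 and the Table 1 footnote agree.

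**Cost.** The changes are to SAP wording, plus a person-time denominator from study-drug start and stop dates and event dates. The rate ratio assumes roughly constant risk over the infusion and does not fully remove the effect of response-dependent stopping. A fixed window such as day 16 (14 days plus 48 hours) would treat the arms alike, but for patients who stop early it needs events later than 48 hours after drug stop. SAP wording cannot supply these if they were not collected, so this cannot be the main remedy. No change to treatment or stopping rules is implied.
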